A feasibility study undertaken by the chief investigator (CI), as part of a PhD programme of study, determined that an ankle placement of the Actigraph GT3X accelerometer was superior to the waist for determination of body position and step count. In this study, thirty healthy adult volunteers simulated patients weakened by critical illness. They performed a movement protocol which incorporated the typical activities undertaken by patients recovering in hospital from critical illness. These included moving from lying to sitting, sitting to standing (and vice versa) and walking short distances. Video recordings were taken of each participant during the movement protocols, enabling observation of the body positions adopted and step counting during the walking activities. Video recording was used as the criterion measure for comparison against the data captured by the accelerometers worn both at the ankle and the waist. The activities detailed above are typically included within early mobility protocols which have undergone evaluation within populations experiencing critical illness (McWilliams et al., 2015, Adler and Malone, 2012, Schweickert et al., 2009). Moderate agreement ($\kappa = 0.43$, $p < 0.001$), was found between observation of video recordings of body position (lying, sitting or standing) and the inclinometer setting for the ankle placement. Fair agreement only ($\kappa = 0.21$, $p < 0.001$) was found for the waist placement. Regular misclassification of all body positions was found with the waist placement. The ankle placement identified both the lying and standing positions well. The sitting position however was only correctly identified intermittently for the ankle placement. A novel finding emerged from this research relating to the ankle placement site. When a side lying position was adopted, the ankle accelerometer inclinometer function regularly registered a '0'. The '0' setting normally corresponds to a 'not being worn' option. When a reading of '0' was recoded to the option 'side lying,' agreement improved from $\kappa = 0.43$ ($p < 0.001$) to $\kappa = 0.48$ ($p < 0.001$). This finding suggests a new way of interpreting the '0' reading of the inclinometer when worn on the ankle, which is worthy of further investigation within an actual patient population.

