Body mass index (BMI) will be calculated by using the latest weight recording (in kilogrammes) on the participants observation charts and asking participants to estimate their height, which will be converted to centimetres if given in feet and inches. Participants will wear two Actigraph GT3X accelerometers, one anteromedially around the mid - thigh and the other around the ankle of the same (ipsilateral) leg resting above the lateral malleolus. The CI will attach the accelerometers, ensuring they feel comfortable and pose no circulatory concerns. The placement sites will be checked on a half hourly basis during the data collection period. This has been recommended by the tissue viability team, to ensure the accelerometers are not compromising skin integrity or circulation. A standardised assessment form will be used for this process, which has been constructed with assistance from the tissue viability team.

The data collection period will not exceed three hours; including rest periods. Accelerometers will be removed at any time during the data collection period should a participant request this. Any data that has been collected during the time period that the accelerometers were worn prior to the request for removal will be downloaded and included within the analysis with the participant's permission.

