Participants will be free to undertake the activities within the semi-structured movement protocol in any order they prefer. Whilst undertaking the movements, participants will be observed by the CI. Although there is a requirement for the CI to be able to visualise them, the actual distance that she is from the patient will be determined according to the individual's wishes. Respect for privacy and dignity will be of paramount importance. Participants will not be observed if they are using a commode, the toilet or if bathing. The accelerometer data downloaded during these periods of time will be excluded from data analysis. A digital clock with an hour, minute and second display, successfully employed within the feasibility study will be used to note the time (to the hour, minute and second) when a particular movement or postural change occurred and ended. Once a postural change ends, a further five seconds will be observed on the digital clock before the new body position is documented as complete. This is to accommodate findings from the feasibility study and subsequent manufacturers recommendations related to how the accelerometer models process information. The digital clock will be synchronised to the time setting on a laptop computer, which will also be used to activate the desired settings on both accelerometers (termed 'initialisation'). These

processes will occur immediately before the data collection period to maximise synchronisation of the digital clock with the time setting on the accelerometers. The laptop computer will not be used during data collection, only for time synchronising the digital clock and for initialising the settings onto both accelerometers. The accelerometers will be programmed to capture data every second (one second epoch).

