A sample size of 20 participants will be recruited. This sample size has been used in previous research investigating the validity of a different accelerometer model to quantify gait parameters in patients recovering from critical illness (Edbrooke et al., 2012). They predicted that 12 subjects were necessary based upon alpha = 0.05 (significance level), beta = 0.9 (power) and a correlation of $r = 0.75$, categorised as a good to excellent correlation (Trapp and Dawson, 2004). A sample size of 20 was also recruited in another study investigating the validity of accelerometer measurement within a hospitalised stroke population (Kramer et al., 2013). Recruiting a sample of 20 patients will permit some attrition should there be any accelerometer malfunction or decisions to withdraw, yet supply an achievable number for participant recruitment based on feedback from clinical colleagues working within the specialty.

Statistical analysis

IBM SPSS statistics (Version 20) will be used to undertake statistical analysis. Some data captured by the accelerometers is continuous and others categorical.

Categorical data

Categorical data, concerning body position (lying, sitting or standing) will be analysed using the Kappa statistic, calculating agreement between the accelerometer inclinometer data and direct observation. Each accelerometer placement site (thigh and ankle) will initially be analysed separately. Examination of the inclinometer raw data captured from both placement sites will determine whether an algorithm can be constructed using readings from both the ankle and thigh placement to improve determination of the sitting

position specifically if necessary. Direct observation will serve as the criterion measure for all the analyses.

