Percentage agreement of inclinometer raw data from the thigh and ankle accelerometers with direct observation for detection of each separate body position will be calculated. A further percentage agreement analysis will be undertaken if an algorithm can be constructed for determination of the sitting position using readings from both placement sites. This algorithm will be compared against direct observational raw data identifying the sitting position only. This result will be compared against the percentage agreement of the individual placement sites in determination of the sitting position. This will assist in determination of whether the algorithm is more superior to a single placement site in determination of the sitting position.

Continuous data

Agreement between step count recorded by each accelerometer placement site and direct observation (manual counts) as a criterion measure will be determined using Bland Altman analysis with 95% limits of agreement (LOA).

Acceptance of the devices over a three-hour period

The statements within the Likert scale will be collapsed to obtain true positives (very comfortable and somewhat comfortable) and true negatives (very uncomfortable and somewhat uncomfortable). The middle category (neither comfortable nor uncomfortable) will remain a separate category. A descriptive analysis will be undertaken to investigate this particular aspect of enquiry using percentages of true positives, the middle category and true negatives. This will be presented graphically.

Any specific comments made by the patients in relation to acceptability of the devices will be included as free text within the results section. The statements will be anonymous and permission from participants will be sought regarding their inclusion within the body of the thesis or publications which may arise from it.

Ethics approval

This study has received approval from the NHS Local Research Ethics Committee (REF: XXXXX) and the Research Ethics Sub Committee, YSJU (REF: XXXXXX).

Data handling and confidentiality

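### Percentage agreement rests on repeated one-second readings from 20 participants and kappa has no stated unit; nothing allows for within-participant correlation, and no interval supports the planned comparisons

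*Combined protocol and SAP*

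**What the plan says.** The sampled unit is the participant. Under Sample size calculation: "A sample size of 20 participants will be recruited". The support is precedent plus a calculation borrowed from an earlier accelerometer study: "They predicted that 12 subjects were necessary based upon alpha = 0.05 (significance level), beta = 0.9 (power) and a correlation of" 0.75. An unquantified allowance for attrition is added.

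The recorded unit is the second. Under Study procedure: "The accelerometers will be programmed to capture data every second (one second epoch". The session may not exceed three hours, and no minimum is set. Periods without observation (toilet, bathing, personal care, time alone) are cut from the analysis. Early removal does not discard a record: "Any data that has been collected during the time period that the accelerometers were worn prior to the request for removal will be downloaded and" analysed if the participant agrees.

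The analysis is under Statistical analysis, Categorical data. Body position "will be analysed using the Kappa statistic, calculating agreement between the accelerometer inclinometer data and direct observation", separately for each site. No unit is given for kappa. For the second measure the text is more specific: "Percentage agreement of inclinometer raw data from the thigh and ankle accelerometers with direct observation for detection of each separate body position will be calculated". If a two-site algorithm can be built, its percentage agreement for sitting is set against that of each single site to judge which is better. The section contains no participant-level summary, weighting rule, method for clustered data, confidence interval or test for either measure.

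**The concern.** The objectives ask whether a placement works in this patient population, whether thigh or ankle is the better single site, and whether the algorithm improves on one site for sitting. All three are statements about patients, and the study has 20 of them. Successive seconds from one patient in one posture are close to copies of each other, so a long recording adds rows without adding patients.

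Two things are at stake. First, one pooled percentage can conceal large differences between patients, and it weights each patient by usable seconds in that posture, which nobody controls. Second, the study will declare a better site or a better algorithm with no valid statement of how far chance could account for the difference. If the default software output is then used to fill that gap, it will treat every row as independent.

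**Working it through.** **1. The plan's own figure.** Inputs from Sample size calculation: alpha 0.05, power 0.9, r = 0.75. Fisher z: n = ((z_alpha + z_power)/atanh(r))² + 3.
- One-sided: ((1.645 + 1.282)/0.973)² + 3 = 12.05, rounded up to 13.
- Two-sided: ((1.960 + 1.282)/0.973)² + 3 = 14.1, rounded up to 15.
- Simulated t-test of r at n = 12: power 0.92 one-sided, 0.86 two-sided.

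So 12 is reproduced closely if the test was one-sided. It assumes one independent pair per participant and concerns a correlation, which this plan does not analyse. It says nothing about the precision of kappa or percentage agreement.

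**2. Number of readings.** At the ceiling: 3 × 3,600 = 10,800 per participant per device, and 20 × 10,800 = 216,000 in all.

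**3. Cost of ignoring clustering.** Design effect = 1 + (m − 1) × ICC, where the ICC is the correlation of correct/incorrect readings within a participant. The documents give no ICC and no expected agreement, so an ICC range and 70% agreement are assumed. The naive 95% half-width is 1.96 × √(0.7 × 0.3/216,000) = 0.19 points. With m = 10,800:

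| Assumed ICC | Design effect | Effective readings (216,000/DE) | SE too small by √DE | True half-width, points |
|---|---|---|---|---|
| 0.01 | 109 | 1,982 | 10.4 | 2.0 |
| 0.05 | 541 | 399 | 23.3 | 4.5 |
| 0.1 | 1,081 | 200 | 32.9 | 6.4 |
| 0.2 | 2,161 | 100 | 46.5 | 9.0 |
| 0.5 | 5,401 | 40 | 73.5 | 14.2 |

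Shorter records reduce the factor but not the problem. At ICC 0.05, 3,600 readings each give a design effect of 181 (factor 13.5), and 600 each give 1 + 599 × 0.05 = 31 (factor 5.6). The effective number stays near 20/ICC = 400, so it is set by participants and not by recording time.

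**4. Kappa itself.** The formula above is for a proportion, so kappa was simulated: 2,000 runs, 20 participants, 1 to 3 hours each, 14 posture bouts each, device reading constant within a bout (all assumed).
- No true agreement: a 5% test on pooled rows rejects in 95% of runs; a leave-one-participant-out jackknife rejects in 5.9%.
- True kappa about 0.53: the pooled-row 95% interval covers it in 4% of runs, the jackknife interval in 93.5%. The mean jackknife standard error is 0.074, so the half-width is 2.093 × 0.074 = 0.15.

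For scale, recoding the zero reading in the feasibility study moved kappa by 0.48 − 0.43 = 0.05. A paired difference can be more precise than a single kappa, but its precision has to be calculated.

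**5. Weighting.** Whole sessions, durations evenly spread (assumed); share = 3/(20 × mean hours), against 5% if equal:
- 2 to 3 h: 3/50 = 6.0%
- 1 to 3 h: 3/40 = 7.5%
- 0.5 to 3 h: 3/35 = 8.6%

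Within one posture the spread can be wider, because participants choose the order, may rest or read, and walk as far as they are able. If time in a posture has a log-SD of 0.7 or 1.0 (assumed), the effective number of participants, (Σt)²/Σt², averages about 13 or 10 of 20.

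**6. What a pooled figure can hide.** With equal seconds, 20 participants at 80% and 16 at 100% with 4 at 0% both give (16 × 100 + 4 × 0)/20 = 80%.

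**The case against.** The plan never says that kappa is computed on pooled seconds. Observation is logged as timed starts and ends of postures, and a kappa per participant or per bout is not excluded. That stands, so the defect in kappa is an unstated unit. It does not rescue the plan: bouts are also repeated within participants, and the percentage-agreement text does refer to raw readings.

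Three stronger readings are tempting, and the documents do not support them.

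- *The plan contains an invalid test.* It plans no test, p-value or standard error for either measure. Kappa p-values appear only in the feasibility results in the background, for example "agreement improved from $\kappa = 0.43$ ($p < 0.001$) to $\kappa = 0.48$ ($p < 0.001"). The warning about p-values is therefore conditional. Nor would clustering necessarily overturn such a result. Take kappa 0.43 and assume chance agreement of 1/3: raw agreement is 1/3 + 0.43 × 2/3 = 0.62, and the pooled SE is √(0.62 × 0.38/216,000)/(2/3) = 0.00157. Multiplied by 73.5 this is 0.115, so kappa still lies about 3.7 standard errors from zero. What is lost is the interval.
- *The longest-recorded patients dominate.* The three-hour cap prevents this under moderate spreads (step 5). It takes an extreme split: five patients at 3 h and fifteen at 0.5 h would give the five 15/22.5 = 67%. The movement checklist, with prompting for missed items, also limits the number of patients with no data in a posture, though it does not equalise time.
- *An equal-weight mean is always more precise.* At ICC 0.2 and log-SD 1.0, with seconds independent given the participant, the sampling SD is 4.0 points against 5.9 pooled. If the device instead stays right or wrong through 60-second bouts at ICC 0.05, it is about 5.1 against 4.3, in favour of pooling. Equal weighting is a choice of what to estimate, so both figures should be shown.

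Finally, this is a small, unfunded doctoral study with largely descriptive statistics. That argues for a light remedy, but it still intends to conclude on a superior site and algorithm.

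**Conclusion.** The concern holds in limited form. The study samples 20 participants, calculates percentage agreement on one-second readings, leaves the unit for kappa unstated, and provides neither an allowance for within-participant correlation nor an interval for its estimates and comparisons. Followed as written, its conclusions on site and algorithm would carry no valid uncertainty, and a failure confined to a few patients could go unseen.

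The size depends on assumptions. The factor of about 23 assumes an ICC of 0.05 and full three-hour records; over ICCs of 0.01 to 0.5 it runs from about 10 to 73, and with ten-minute records at 0.05 it is about 6. It would distort results only if standard errors, intervals or p-values were taken from pooled rows, which the plan neither proposes nor rules out. Unequal weighting is real but modest over whole sessions; it may be larger within a posture, and the documents give no figure for that.

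**What to change.** Amend Statistical analysis, Categorical data, as follows.

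1. State the unit of analysis for kappa and for percentage agreement.
2. For each site, and for the two-site algorithm if one is built, calculate agreement by position within each participant. Report the individual values and their range, the seconds observed, and the number of participants with data in that position, beside the pooled figure.
3. Give 95% intervals for kappa, for percentage agreement, and for the paired differences (thigh against ankle, algorithm against each single site) by resampling whole participants, never rows. A leave-one-participant-out jackknife is a simple alternative that needs at most 20 repeats of the same calculation.
4. Do not report the ordinary kappa p-value or standard error from pooled readings.

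The cost is a paragraph of text, one aggregation step and a short resampling routine on data already to be collected; no extra patients, procedures or staff. The stated uncertainty will be wider, and participants with little time in a posture will give noisy values, which is why the seconds should be shown beside them.

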3. To investigate the criterion validity of the combination of thigh and ankle accelerometer inclinometer outputs to correctly determine the sitting position. This

will determine whether an algorithm can be constructed using the two inclinometer readings, which will better distinguish the sitting from the standing position.

4. To evaluate, from a user perspective, the acceptability of these devices in relation to the placement sites used. This will be achieved by asking patients to score the answer to a particular question through the use of a Likert scale. The question is:
 - How would you rate the comfort of wearing the accelerometers?

In consideration of the results from the feasibility study undertaken by the CI and research using the addition of a thigh mounted accelerometer to identify the sitting position (Skotte et al., 2014), the following hypotheses can be constructed:

Hypotheses

1. An ankle mounted Actigraph GT3X accelerometer, will accurately identify both the lying and standing positions when compared with direct observation as a criterion measure.
2. An ankle mounted Actigraph GT3X accelerometer, will capture a step count comparable to that recorded by direct observation in a population resident on a hospital ward recovering from critical illness.
3. The combination of inclinometer outputs of both the thigh and ankle placement sites will permit development of an algorithm permitting the ability to better distinguish between the sitting and standing position.
4. The ankle and mid-thigh accelerometer placement sites will be well tolerated by patients recovering on a ward from critical illness.

Subject selection and involvement

The study will invite adult hospital ward patients recovering from critical illness to wear one Actigraph GT3X accelerometer on the antero-medial mid-thigh and another on the ankle, resting above the lateral malleolus of the same leg. The accelerometers will be worn for a period of time not exceeding three hours. Each device will be attached with a single patient use broad elastic belt, secured by Velcro fastening, using a standardised placement protocol. The non – dominant leg will be the preferred placement side.

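### Percentage agreement per body position has no defined denominator and, on its natural reading, cannot show sitting misread as standing, so a conclusion on Hypothesis 1 could rest on a figure that ignores false standing

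*Combined protocol and SAP*

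**What the plan says.** Hypothesis 1 (Hypotheses) states that an ankle-mounted device "will accurately identify both the lying and standing positions when compared with direct observation as a criterion measure". It names no statistic and sets no threshold.

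Statistical analysis, Categorical data, plans two things for each single site:

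- Body position "will be analysed using the Kappa statistic, calculating agreement between the accelerometer inclinometer data and direct observation". The two sites are first taken one at a time.
- Percentage agreement of the raw inclinometer data "with direct observation for detection of each separate body position will be calculated". The denominator is not defined.

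For the possible two-site algorithm, the same section says: "This algorithm will be compared against direct observational raw data identifying the sitting position only".

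No observed-by-device table, specificity, predictive value or standing-specific kappa is planned.

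The feasibility study, described under The Actigraph GT3X accelerometer, reports an ankle kappa of 0.43. It says of the ankle: "The ankle placement identified both the lying and standing positions well". It then adds: "The sitting position however was only correctly identified intermittently for the ankle placement". Objective 3 and Hypothesis 3 name sitting versus standing as the distinction that needs improving.

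**The concern.** To say that a sensor identifies standing accurately is to say two things: it reads standing when the patient stands, and it does not read standing when the patient is doing something else. The planned percentage agreement, on its natural reading, addresses only the first. The word detection points to that reading. So does the restriction of the algorithm comparison to observed sitting.

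The missing half is the error the protocol leads one to expect. Sitting that the ankle fails to recognise must be given some other reading, and Hypothesis 3 treats standing as the competing category. The feasibility report already shows how this can play out: standing was called well identified alongside intermittent recognition of sitting and a kappa of 0.43.

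The introduction wants the device to find patients with prolonged inactivity, so that rehabilitation effort can be directed to them. A seated patient recorded as standing is the error that would work against that use.

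**Working it through.** The documents contain no figure to reproduce on this point. The feasibility cross-table behind the kappa of 0.43 is not given, and neither are minutes per position or misreading rates. The check is therefore an illustration on stated assumptions.

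**Assumed inputs.** 60, 60 and 10 minutes observed lying, sitting and standing (130 in total, within the three-hour limit in Study procedure). 95% of lying and of standing read correctly, with those errors read as sitting. Half of sitting misread, either as standing (case A) or as lying (case B).

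**Tables (minutes).**

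| Observed | A: lying / sitting / standing | B: lying / sitting / standing |
|---|---|---|
| Lying 60 | 57 / 3 / 0 | 57 / 3 / 0 |
| Sitting 60 | 0 / 30 / 30 | 30 / 30 / 0 |
| Standing 10 | 0 / 0.5 / 9.5 | 0 / 0.5 / 9.5 |

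**Formulas.** Agreement for a position = correct minutes / observed minutes in it. Kappa = (po - pe) / (1 - pe). Specificity for standing = non-standing minutes not read as standing / all non-standing minutes. Share of standing readings that are true = true standing readings / all standing readings.

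| Measure | A | B |
|---|---|---|
| Agreement: lying, sitting, standing | 95%, 50%, 95% | 95%, 50%, 95% |
| po | 96.5/130 = 0.742 | 96.5/130 = 0.742 |
| pe | 5825/16900 = 0.345 | 7325/16900 = 0.433 |
| Kappa | 0.61 | 0.55 |
| Specificity for standing | 90/120 = 75% | 120/120 = 100% |
| Share of standing readings true | 9.5/39.5 = 24% | 9.5/9.5 = 100% |

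The three planned percentages are identical in A and B. Kappa is higher in A, the case whose standing output is less trustworthy. The planned statistics do not separate the two cases.

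**Dependence on the assumptions.**

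- If the 3 misread lying minutes in A go to standing instead of sitting, 42.5 minutes are read as standing, specificity is 1 - 33/120 = 72.5%, and the true share is 9.5/42.5 = 22%.
- At 60/60/60 minutes the true share is 57/87 = 66%, or 57/90 = 63% with lying errors sent to standing. Specificity is unchanged at 75% or 72.5%.
- At 60/90/15 minutes, specificity is 1 - 45/150 = 70%; at 90/60/10 it is 1 - 30/150 = 80%. The true share is 24% in both.
- At 60/90/15, letting the misread share of sitting run from 0% to 90% moves kappa from 0.96 to 0.34. Standing agreement stays at 95% throughout.

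**A caution on the share of standing readings that are true.** At 60/60/10, take a sensor that reads 95% of every position correctly, with all misread lying and sitting going to standing. Its true share is only 9.5/(9.5 + 3 + 3) = 61%, while its specificity is 114/120 = 95%. With no sitting misread and 3 lying minutes read as standing, the share is still only 9.5/12.5 = 76%. The figure falls when little standing is observed, even for a good sensor.

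**The case against.** A reader might infer that Hypothesis 1 is to be judged on the share of observed standing read correctly, so that a sensor reading standing through much of chair sitting would be declared accurate. The documents do not say that. Hypothesis 1 is tied to no statistic, kappa is planned for each site, and no decision rule exists.

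The denominator is also an inference. The sentence about sitting only concerns the algorithm, so it supports the reading for single sites without settling it. If agreement means standing versus not standing, false standing does count: case A gives (9.5 + 90)/130 = 77%.

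Nor would the plan conceal the problem altogether. Ankle sitting agreement would appear as 50% beside standing at 95%, and kappa would fall. The weakness in sitting is openly acknowledged and has its own objective. The feasibility account does not say whether misread sitting was recorded as standing, lying or 0.

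Finally, a reader might infer that most standing readings would really be sitting. That depends on the time mix: it is so at 60/60/10 in case A, but not at 60/60/60.

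All of this stands, and it limits the point to a risk. It does not remove the gap. With the denominator undefined, the more favourable version could be adopted after the data are seen. Low sitting agreement and a lower kappa still do not say whether a standing reading can be believed.

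**Conclusion.** The point holds as a gap in the measure. The only position-specific single-site statistic is undefined and, on its most natural reading, blind to sitting read as standing. Neither kappa nor the sitting agreement fills the gap, because neither shows where the misread time went. Hypothesis 1 for standing could therefore be concluded from a favourable figure that leaves out false standing; nothing written in the plan requires that conclusion.

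The size is illustrative only. With half of sitting read as standing at 60/60/10 minutes, a reported 95% would go with specificity of about 72-75% and about 22-24% true standing readings. The direction does not depend on the assumed times or rates; the size does. The same limitation applies to lying if sitting is misread as lying: in case B lying agreement is 95%, while specificity for lying is 40/70 = 57%.

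**What to change.** In Statistical analysis, Categorical data:

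1. Define the denominator of percentage agreement.
2. For each site, report the full table of observed position by device reading, including reading 0, which the device can return (Data collection process) and which the feasibility study saw regularly at the ankle in side lying.
3. For each position give sensitivity and specificity, and base the Hypothesis 1 conclusion for lying and for standing on both. State before the data are seen how the two will be weighed; the documents offer no threshold and none is proposed here.
4. Report the share of device readings that are correct as a descriptive figure, noting that it depends on the observed time mix. Do not use it as a pass/fail rule, because participants choose the order of movements and their walking distance is set by ability. Specificity also shifts somewhat with the balance of lying and sitting, so the full table should accompany it.

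The cost is a few lines of analysis text. The same cross-table already underlies kappa, and no new data are needed. The downside is that the standing result may look less favourable.
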